7.4 SCREENING

Participating study sites are required to document all screened subjects considered for inclusion in this study. If a subject is excluded from the study, the reasons for exclusion will be documented in the subject's source documents and noted on the Screening and Enrollment Log. All screening activities that occur prior to consent shall be referred to as pre-screening.

7.5 INFORMED CONSENT

Before conducting any study procedures or examinations, the purpose and nature of the study should be explained to the subject. The subject, will then **read, sign, and personally date** the EC-approved informed consent document(s). Additionally, the individual who obtains consent from the subject will sign and date the informed consent document. A copy of the signed informed consent document will be provided to the subject, a copy will be placed in the subject's medical record, with the original filed in the Investigator Site File (ISF).

7.6 ENROLMENT

The point of enrolment into the study is when the subject has signed and dated the informed consent document and met all the eligibility criteria.

The anticipated enrolment period for 40 subjects is thirteen (13) months. Once the subject is enrolled a subject ID number will be assigned as a unique study identifier.

7.7 LOST TO FOLLOW-UP

Some actively enrolled subjects will not return for follow-up exams on time. Study personnel must make a reasonable effort to contact the subject and document the following contact attempts

CONFIDENTIAL AND PROPRIETARY

This document contains information that is confidential and proprietary to Smith & Nephew PLC and Smith & Nephew, Inc. and is intended for use only by Smith & Nephew and its manufacturer. It shall not be reproduced or copied in whole or in part, nor shall the contents be disclosed by any means without prior written permission from Smith & Nephew, nor shall anyone make any use of it that is contrary to the expressed or implied wishes of Smith & Nephew.

| | |
|--|---|
| Study Protocol—Device |  |
| A Prospective, Multi-center, Post-Market Clinical Follow-Up Study to Evaluate the Safety and Effectiveness of ALLEVYN Gentle Border | Number: ALLEV.PMCF.2017.13 |
| | Version: 3.0 |
| | Date: 21 JUN 2019 |
| | Page: Page 31 of 90 |

before declaring a subject to be lost to follow-up: the subject has been contacted according to the site's policies, but no fewer than two documented phone contacts and one certified letter without response. Copies of all attempts to reach the subjects by mail or email and/or the attempts to contact the subject via other means should be documented, and that documentation should be kept with the subject's source documents.

7.8 WITHDRAWAL

7.8.1 Withdrawal from Treatment

If a subject is withdrawn from study treatment the Treatment Discontinuation Case Report Form (CRF) needs to be filled out. However, the subjects will be followed up to the end of the study for safety assessments until day 28 (\pm 3 days).

Subjects may be withdrawn early from study treatment based on the decision of the investigator. This might include but is not limited to the following reasons:

- Closure of the reference wound
- Worsening condition of reference wound
- If the subject misses two (2) consecutive dressing changes/study visits, interrupting treatment for longer than seven (7) days
- A change in treatment that is clinically warranted
- An adverse event (AE)
- Concurrent illness
- Adverse device effects (ADE)
- Non-compliance (e.g. did not follow instructions)
- Lost to follow-up (LTFU)
- Any other significant reason identified by the Investigator

CONFIDENTIAL AND PROPRIETARY

This document contains information that is confidential and proprietary to Smith & Nephew PLC and Smith & Nephew, Inc. and is intended for use only by Smith & Nephew and its manufacturer. It shall not be reproduced or copied in whole or in part, nor shall the contents be disclosed by any means without prior written permission from Smith & Nephew, nor shall anyone make any use of it that is contrary to the expressed or implied wishes of Smith & Nephew.

| | |
|--|---|
| Study Protocol—Device |  |
| A Prospective, Multi-center, Post-Market Clinical Follow-Up Study to Evaluate the Safety and Effectiveness of ALLEVYN Gentle Border | Number: ALLEV.PMCF.2017.13 |
| | Version: 3.0 |
| | Date: 21 JUN 2019 |
| | Page: Page 32 of 90 |

Any subject that does not meet the minimum reference wound size requirement following wound size tracing at Visit 1 will be withdrawn. Subjects withdrawn from the study for this reason alone shall be replaced by enrolment of a new study subject. A new subject number will be assigned.

7.8.2 Subject’s Withdrawal of Consent to Participate in Study

Study participation is voluntary, and subjects may withdraw at any point during the study without giving their reason for doing so. Where subjects withdraw consent, the Investigator should make a reasonable effort to ascertain the reason(s), while fully respecting the subject’s privacy. The reason for withdrawal will be recorded in the CRF and source documents.

7.8.3 Use of Data Following Withdrawal

In cases where the subject withdraws consent, the data collected up to the point of withdrawal may be used, but no additional data for that subject may be collected.

8. STUDY DESIGN

8.1 STUDY DESIGN

This is a non-randomized, open label study in up to 8 study centres at maximum, conducted in up to 3 countries in Europe. The sample size is 40 subjects. There is no comparator group, however, subjects will be consecutively enrolled into 2 wound groups: A minimum of 10 subjects with acute wounds and a minimum of 10 subjects with chronic wounds.

Participation in the study will last 4 weeks (28±3 days) for each subject. All subjects will receive ALLEVYN Gentle Border as the study device, there is no control group. Subjects will be required to make at least one visit per week to the study center.

In total, 5 study visits are planned for each subject (day 0, day 7, day 14, day 21, day 28). The primary clinical endpoint (reduction of wound size) will be assessed at each study visit by using a specific camera. This camera will make a photograph of the wound in a standardized manner and will calculate the wound length, wound width and the depth of the wound automatically.

CONFIDENTIAL AND PROPRIETARY

This document contains information that is confidential and proprietary to Smith & Nephew PLC and Smith & Nephew, Inc. and is intended for use only by Smith & Nephew and its manufacturer. It shall not be reproduced or copied in whole or in part, nor shall the contents be disclosed by any means without prior written permission from Smith & Nephew, nor shall anyone make any use of it that is contrary to the expressed or implied wishes of Smith & Nephew.

| | |
|--|---|
| Study Protocol—Device |  |
| A Prospective, Multi-center, Post-Market Clinical Follow-Up Study to Evaluate the Safety and Effectiveness of ALLEVYN Gentle Border | Number: ALLEV.PMCF.2017.13 |
| | Version: 3.0 |
| | Date: 21 JUN 2019 |
| | Page: Page 33 of 90 |

8.1.1 Treatment Allocation

This study is not randomized.

8.1.2 Blinding

This study is an open label post-market clinical follow-up study.

8.2 STUDY ENDPOINTS

8.2.1 Primary Endpoint

The absolute reduction in wound area from baseline to end of study visit.

8.2.2 Secondary Endpoints

- Absolute reduction in area from baseline to days 7(+/-3), 14 (+/-3), 21 (+/-3)
- Absolute reduction in depth and volume from baseline to visits 2, 3, 4 and end of study visit
- Percentage reduction in area, depth and volume from baseline visit to visits 2, 3, 4 and end of study visit
- Exudate management (fluid handling ability including leakage and percentage strikethrough)
- Exudate type, amount and viscosity
- Odour control – during wear and during dressing change
- Dressing change frequency
- Condition of surrounding skin
- Signs of clinical infection
- Healing of reference wound
- Dressing wear time
- Dressing retention, presence of bunching up and percentage dressing lift
- Comfort during wear
- Showerproof qualities
- Pain on application, during treatment and on dressing removal

CONFIDENTIAL AND PROPRIETARY

This document contains information that is confidential and proprietary to Smith & Nephew PLC and Smith & Nephew, Inc. and is intended for use only by Smith & Nephew and its manufacturer. It shall not be reproduced or copied in whole or in part, nor shall the contents be disclosed by any means without prior written permission from Smith & Nephew, nor shall anyone make any use of it that is contrary to the expressed or implied wishes of Smith & Nephew.

| | |
|--|---|
| Study Protocol—Device |  |
| A Prospective, Multi-center, Post-Market Clinical Follow-Up Study to Evaluate the Safety and Effectiveness of ALLEVYN Gentle Border | Number: ALLEV.PMCF.2017.13 |
| | Version: 3.0 |
| | Date: 21 JUN 2019 |
| | Page: Page 34 of 90 |

Patient Reported Outcome (PRO):

- To assess the change from baseline in subject reported outcomes using the Cardiff Wound Impact Schedule (CWIS)

Safety Performance:

- All Adverse Events and Device Deficiencies

8.2.3 Other Endpoints

Not applicable.

8.3 METHODS USED TO MINIMIZE BIAS AND MAXIMIZE VALIDITY

The study will be conducted across multiple centres and subjects will be enrolled by wound type to safeguard against major imbalances in clinical characteristics at baseline and aid comparability between the wound groups.

9. STUDY PROCEDURES

9.1 VISITS AND EXAMINATIONS

9.1.1 Summary

All subjects receive the ALLEVYN Gentle Border study device at visit 1 (Baseline, day 0). In total, all subjects need to perform 5 key study visits between week 1 and week 4, as shown in table 1. The visit schedule is based on the 7 days of maximum dressing wear time of ALLEVYN Gentle Border. The key visit date is counted from Baseline (day 0) and usually occurs on the same weekday in the following week. If a dressing change is required between the key visits the subject should come to an interim on-site visit (Routine Dressing Change Visit). A routine dressing change assessment will then be performed and documented in the Case Report Form. Then the subject

CONFIDENTIAL AND PROPRIETARY

This document contains information that is confidential and proprietary to Smith & Nephew PLC and Smith & Nephew, Inc. and is intended for use only by Smith & Nephew and its manufacturer. It shall not be reproduced or copied in whole or in part, nor shall the contents be disclosed by any means without prior written permission from Smith & Nephew, nor shall anyone make any use of it that is contrary to the expressed or implied wishes of Smith & Nephew.

| | |
|--|---|
| Study Protocol—Device |  |
| A Prospective, Multi-center, Post-Market Clinical Follow-Up Study to Evaluate the Safety and Effectiveness of ALLEVYN Gentle Border | Number: ALLEV.PMCF.2017.13 |
| | Version: 3.0 |
| | Date: 21 JUN 2019 |
| | Page: Page 35 of 90 |

continues with the next study key visit, counted from Baseline. If a subject is withdrawn from AGB treatment prior to key visit 5, this subject is still regarded as an active study participant. He/she should continue to come to the study key visit to follow-up with patients' safety up to visit 5.

9.1.2 Study Visit 1 - Initial Visit (Baseline Visit, day 0)

The following assessment will be performed at Visit 1.

1. Obtain written informed consent from the subject as detailed in Section 7.5.

----- Do not proceed until consent has been obtained -----
2. Screen the subject for protocol inclusion/exclusion criteria and identify the study wound as the "reference wound" (if more chronic wounds are present per subject).
3. Assign the subject to a study number.
4. Provide the subject with the pages of CWIS and Patient Pain Scale, and allow sufficient time to complete it.
5. Classify the wound type and perform wound assessment according to the Bates-Jensen Wound Assessment Tool (BWAT), as outlined in chapter 9.2.4.
6. **Photograph the wound** with the delivered digital camera (Silhouette) and make sure that the image is assigned to the correct patient.
7. Apply ALLEVYN Gentle Border dressing on the wound.
8. Record details of the size and order number of ALLEVYN Gentle Border (including dressing cut, if performed). ALLEVYN Gentle Border can be cut and an aseptic technique should be used with cutting the dressing. Ensure any exposed foam areas are covered with an appropriate film dressing taking care not to cover the entire dressing.
9. Assess the ease of applying the dressing, including remains in place and repositioning (if applicable).
10. Instruct the subject to carefully follow the standard care instructions until the next dressing change and provide information concerning arrangements for future study visits. Subjects should return to the study center for the next study visit in 7 days (± 3), or earlier if a dressing change is required.

CONFIDENTIAL AND PROPRIETARY

This document contains information that is confidential and proprietary to Smith & Nephew PLC and Smith & Nephew, Inc. and is intended for use only by Smith & Nephew and its manufacturer. It shall not be reproduced or copied in whole or in part, nor shall the contents be disclosed by any means without prior written permission from Smith & Nephew, nor shall anyone make any use of it that is contrary to the expressed or implied wishes of Smith & Nephew.

| | |
|--|---|
| Study Protocol—Device |  |
| A Prospective, Multi-center, Post-Market Clinical Follow-Up Study to Evaluate the Safety and Effectiveness of ALLEVYN Gentle Border | Number: ALLEV.PMCF.2017.13 |
| | Version: 3.0 |
| | Date: 21 JUN 2019 |
| | Page: Page 36 of 90 |

- | |
|---|
| 11. Record the total time that the subject spent at the visit (start to finish of wound care procedures). |
|---|

9.1.3 Study Visit 2 (day 7, ±3), Visit 3 (day 14, ±3), Visit 4 (day 21, ±3)

Visits 2 - 4 will be performed as on-site visits, so the subjects need to be present at each key study time point. These visits should take place every seventh (7) day. In case a dressing change is required before day 7, the instructions for a Routine Dressing Change Visit need to be followed (chapter 9.1.4).

Subjects who are already withdrawn from treatment and no longer require a dressing change shall be followed up on the study visits to collect safety information.

- | |
|---|
| 
 1. Question subjects regarding any changes in health or concomitant treatment. 2. Hand out the CWIS, Patient Assessment Scale and Pain Scale to the subject and allow sufficient time to complete it. 3. Photograph the dressing in situ prior to removal with the delivered digital camera. 4. Remove the old dressing and inspect the wound. Complete a wound assessment according to BWAT (see Section 9.2.4). 5. Assess the reason for dressing change, assess the ease of dressing removal and dressing leakage. 6. Record any debridement and the method of debridement, and take a photograph of the wound immediately prior to and following debridement. Note: Photographs are not necessary if the subject was withdrawn from treatment at a previous visit. 7. Redress the wound, if clinically indicated. 8. Record details of all dressings used (e.g. brand, size, etc.) as well as any treatment applied underneath the dressing. |
|---|

CONFIDENTIAL AND PROPRIETARY

This document contains information that is confidential and proprietary to Smith & Nephew PLC and Smith & Nephew, Inc. and is intended for use only by Smith & Nephew and its manufacturer. It shall not be reproduced or copied in whole or in part, nor shall the contents be disclosed by any means without prior written permission from Smith & Nephew, nor shall anyone make any use of it that is contrary to the expressed or implied wishes of Smith & Nephew.

| | |
|--|---|
| Study Protocol—Device |  |
| A Prospective, Multi-center, Post-Market Clinical Follow-Up Study to Evaluate the Safety and Effectiveness of ALLEVYN Gentle Border | Number: ALLEV.PMCF.2017.13 |
| | Version: 3.0 |
| | Date: 21 JUN 2019 |
| | Page: Page 37 of 90 |

9. Assess the ease of applying the new dressing, including remains in place and repositioning (if applicable).
10. Instruct the subject to carefully follow the ulcer care instructions until the next dressing change and provide information concerning arrangements for future study visits.
11. Record the total time that the subject spent at the visit (start to finish of ulcer care procedures).
12. If any AE or DevD are observed or reported after application of study product, they must be reported as instructed in Section 12 (Adverse Events and Device Deficiencies).

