9.1.4 Routine Dressing Change Visit (between key study visits, if required)

As ALLEVYN Gentle Border has a maximum recommended wear time of 7 days, routine dressing changes might occur between scheduled study visits. **Dressings should not be given to study subjects; the dressing should only be changed by the investigator or delegated person.**

If a subject requires dressing change in between a study visit, the following assessments will be performed.

1. Question subjects regarding any changes in health or concomitant treatment.
2. Ask the subject to assess the comfort of wearing the dressing since the last visit.
3. Photograph the dressing in situ prior to removal with the delivered digital camera.
4. Remove the old dressing, inspect the wound and complete wound assessment according to BWAT (see Section 9.2.4).
5. Assess the reason for dressing change, assess the ease of dressing removal and dressing leakage.
6. Record any debridement and the method of debridement, and **take a photograph of the wound immediately prior to and following debridement.**
7. Assess the level of pain experienced by the subject when the dressing is removed.

CONFIDENTIAL AND PROPRIETARY

This document contains information that is confidential and proprietary to Smith & Nephew PLC and Smith & Nephew, Inc. and is intended for use only by Smith & Nephew and its manufacturer. It shall not be reproduced or copied in whole or in part, nor shall the contents be disclosed by any means without prior written permission from Smith & Nephew, nor shall anyone make any use of it that is contrary to the expressed or implied wishes of Smith & Nephew.

| | |
|--|---|
| Study Protocol—Device |  |
| A Prospective, Multi-center, Post-Market Clinical Follow-Up Study to Evaluate the Safety and Effectiveness of ALLEVYN Gentle Border | Number: ALLEV.PMCF.2017.13 |
| | Version: 3.0 |
| | Date: 21 JUN 2019 |
| | Page: Page 38 of 90 |

8. Redress the wound, if clinically indicated.
9. Record details of all dressings used (e.g. brand, size, etc.) as well as any treatment applied underneath the dressing.
10. If any adverse events or device deficiencies are observed or reported, they must be recorded as instructed in Safety Section 12.
11. Redress the wound with ALLEVYN Gentle Border.
12. Record details of the new ALLEVYN Gentle Border dressing.

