9.2.6 Patient Pain Scale (PPS)

During the AGB treatment phase, the patient will be asked to describe the level of pain during the application, during AGB treatment and on removal of the dressing on a scale from 0 (no pain) to 10 (worst pain). The subject will be asked to draw a vertical line on this visual scale to indicate the value. The value will be rounded to a whole number and transmitted into the CRF by the investigator. The PPS will be entered directly into the case report form and will serve as source data.

CONFIDENTIAL AND PROPRIETARY

[figure not shown]
This document contains information that is confidential and proprietary to Smith & Nephew PLC and Smith & Nephew, Inc. and is intended for use only by Smith & Nephew and its manufacturer. It shall not be reproduced or copied in whole or in part, nor shall the contents be disclosed by any means without prior written permission from Smith & Nephew, nor shall anyone make any use of it that is contrary to the expressed or implied wishes of Smith & Nephew.

| | |
|--|---|
| Study Protocol—Device |  |
| A Prospective, Multi-center, Post-Market Clinical Follow-Up Study to Evaluate the Safety and Effectiveness of ALLEVYN Gentle Border | Number: ALLEV.PMCF.2017.13 |
| | Version: 3.0 |
| | Date: 21 JUN 2019 |
| | Page: Page 46 of 90 |

[figure not shown]
Level of pain experienced by the subject on application of the dressing

Level of pain experienced by the subject during treatment with AGB

Level of pain experienced by the subject on removal of the dressing

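### At Visits 2–4 and End of Study the patient completes the Pain Scale while the old dressing is still on, so its removal item cannot describe that visit's removal

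*Combined protocol and SAP*

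**What the plan says.** Section 8.2.2 lists pain at application, during treatment and at removal as a secondary endpoint. Section 9.2.6 defines the Pain Scale: the patient is asked to "describe the level of pain during the application, during AGB treatment and on removal of the dressing", each from 0 to 10. It gives no recall period or time of completion, and does not say which dressing each item concerns.

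The visit instructions are numbered lists:

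- **Visits 2–4 (9.1.3).** Step 2: "Hand out the CWIS, Patient Assessment Scale and Pain Scale to the subject and allow sufficient time to complete it". Step 3: "Photograph the dressing in situ prior to removal with the delivered digital camera". Step 4: "Remove the old dressing and inspect the wound". Step 7: "Redress the wound, if clinically indicated".
- **End of Study (9.1.5).** The scale is again step 2, the photograph of the dressing in place step 3 and removal step 4. No redressing step is listed.
- **Visit 1 (9.1.2).** Step 4: "Provide the subject with the pages of CWIS and Patient Pain Scale, and allow sufficient time to complete it". Step 7: "Apply ALLEVYN Gentle Border dressing on the wound".
- **Routine dressing change (9.1.4).** The dressing comes off at step 4. Step 7: "Assess the level of pain experienced by the subject when the dressing is removed".

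Section 9.2.8 includes pain (application, treatment, removal) among the investigator's assessments at each study visit, without timing. Section 10.4.2 plans summaries of the pain endpoint at study visits and at routine changes. Section 10.3 plans baseline summaries for all primary and secondary endpoints.

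**The concern.** A rating of removal pain describes a removal only if it is given during or after it. At Visits 2–4 and End of Study the list has the patient finish the form, then has the dressing photographed while still worn, and only then has it removed. The patient must therefore anticipate the coming removal, recall an earlier one, or leave the item blank. The protocol does not say which.

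Routine changes use the opposite order. A removal score from a routine change and one from a key visit may then refer to different things under the same label.

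At stake is the meaning of a named patient-reported endpoint in a single-arm study. Section 4 describes the new wound contact layer as non-adherent and as sparing epidermal cells and healing tissue. Removal pain is one of the patient-reported items closest to that description, and there is no control arm in which the same measurement problem would also appear.

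**Working it through.** No arithmetic beyond counting applies. The check sets the step numbers in 9.1.2 to 9.1.5 beside what 9.2.6 asks.

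| Visit | Patient pain rating at step | Removal at step | Study-dressing application at step |
|---|---|---|---|
| Visit 1 | 4 | none | 7 |
| Visits 2–4 | 2 | 4 | 7 (if redressed) |
| End of Study | 2 | 4 | none |
| Routine change | 7 (removal pain only) | 4 | 8 and 11 |

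1. **Removal item, key visits.** Removals are listed at Visits 2, 3, 4 and 5, so 3 + 1 = 4. In all four the rating (step 2) precedes the removal (step 4). The photograph at step 3 confirms that the dressing is still on. No later step at these visits asks the patient to rate pain.

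2. **Subject with no routine changes.** None of the four removals is rated by the patient when it happens. If the item is read as recall, those at Visits 2, 3 and 4 could be rated at the next visit, nominally 7 days later. The End of Study removal has no next visit, so no patient rating on the scale can describe it. At Visit 2 there is no earlier study-dressing removal to recall, so the item has nothing to refer to.

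3. **Application item.** At Visit 1 the scale (step 4) precedes the first study application (step 7), so an application score cannot concern the study dressing, and neither can a during-treatment score. At Visits 2–5 the subject is wearing a dressing already applied, so the item can be answered as recall of that application. Section 9.2.6 does not say whether this is intended.

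4. **Routine changes.** Removal pain is assessed three steps after removal (7 − 4 = 3), at the same visit. Table 1 ticks the Pain Scale for these visits, but the step list names removal pain only.

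5. **Analysis.** Section 10.4.2 covers both visit types. It gives no rule for distinguishing scores given after the event from recalled or anticipated ones.

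**The case against.** **The lists are not declared a strict sequence.** The only explicit stop is for consent in 9.1.2, and 9.1.4 lists redressing twice (steps 8 and 11), so its numbering is not a clean chronology. No step collects the form, so a site could hold it back until after removal. This stands as a limit: what sites do is not known. But nothing tells them to hold the form, and sites resolving it differently would add inconsistency.

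**Section 9.2.8 already requires a pain evaluation.** It does, at each study visit and including removal. A reader might infer that the End of Study removal is never rated by anyone; 9.2.8 does not allow that inference. What holds is narrower: there is no later *patient* rating on the scale. The investigator item has no timing, so it does not resolve the order, and the plan does not say whether the summaries draw on it, on the Pain Scale or on both.

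**Application ratings may be valid recall.** A reader might infer that both application and removal pain are scored before they occur at every key visit. That goes too far. Visit 1 has no study-dressing removal, End of Study has no redressing, and at Visits 2–5 the application item can refer to the dressing being worn.

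**Pooling is not stated.** A reader might take 10.4.2 to merge key-visit and routine scores. It specifies summaries at both visit types, by wound type and overall, and does not say the two are combined.

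**Visit 1 may be a deliberate baseline.** Version 3.0 dropped the Patient Assessment Scale at baseline as better suited to use after treatment (21.1.2) but kept the Pain Scale, and 10.3 plans baseline summaries. This is plausible, and the fix must allow for it. It sits poorly with 9.2.6, which places the scale in the treatment phase and words one item around treatment with the study dressing.

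**No pain claim is named.** Section 5.3 refers only to performance and safety evidence in general. The pain endpoint should not be described as carrying a specific claim.

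**Conclusion.** The point holds for the patient's removal rating at all four key-visit removals, and for application and treatment ratings of the study dressing at Visit 1. It rests on one assumption: that sites follow the steps in the order listed. For application ratings at Visits 2–5 the finding is only that the reference dressing is undefined. The same endpoint is collected at two timings, and 10.4.2 reports both without distinguishing them.

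The documents give nothing from which to estimate the size or direction of the error in the scores. The endpoint is secondary, and 10.4.2 specifies summaries for it and no test. The primary endpoint and sample size are unaffected. The change should be made because it is cheap and because a removal not rated at the time cannot be recovered later.

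**What to change.** - **9.1.3 and 9.1.5.** Keep the CWIS, the Patient Assessment Scale and the during-treatment pain item before removal. Have the patient complete the removal item immediately after the old dressing comes off. At Visits 2–4, have the patient complete the application item immediately after redressing.
- **9.1.4.** Use the same timing at routine changes, and list the application and during-treatment items as well as removal.
- **9.2.6.** State which dressing each item concerns and when it is completed.
- **9.1.2.** Rate study-dressing application pain after step 7. If a pre-treatment rating is kept, label it as a baseline for the prior dressing, consistent with 10.3. Do not report it as removal or treatment pain for the study dressing.
- **9.2.8 and 10.4.2.** State when the investigator's pain evaluation is made and which source feeds the summaries. Report scores collected under the present order separately from those collected after the change.

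The cost is a reordering of steps, a CRF note and a short site instruction, with no added visit or procedure. Section 11 records 10 subjects enrolled under Version 2.0 as at 19 June 2019, against a target of 40. On that count 40 − 10 = 30 subjects could still be measured under the revised timing.
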